1.3 SCHEDULE OF ACTIVITIES (SOA)

	Visit 1 Screening ^a -28 days max	Visit 2 Surgery	Visit 3 Day 4	Visit 4 Day 8	Visit 5 Day 15 (EOS)
Signed written	x				
informed consent	Λ				
Demography	X				
Medical history	X				
Inclusion/exclusion	v	v			
criteria	Λ	Λ			
Concomitant	v	v	v	v	v
medications	Λ	Λ	Λ	Λ	Λ
Urine pregnancy test ^b		X			
Surgery		Х			
Randomization ^c		X			
Dispensation of		v		\mathbf{v}^{f}	
treatment and diary		Λ		Λ	
Slit lamp examination ^d	X		Х	Х	Х
TOSS			Х	Х	Х
Diagnosis of endophthalmitis			Х	Х	X
Ocular pain and			Х	Х	X
			V	V	V
Use of rescue therapy	V		$\frac{\Lambda}{\mathbf{v}}$		A V
Intraocular pressure	Λ		Λ	Λ	Λ
Visual acuity (as per local practice)	X				Х
Local tolerability ^e			X	X	X
Adverse events	X	X	X	X	X
Return of treatment				X	X
Return of					
diary/compliance			Х	X	Х

TOSS = Total Ocular Symptoms Score; EOS = End of Study

Additional visits may be scheduled in case of patient need.

^a Screening to be performed not more than 28 days prior to surgery

^b A urine pregnancy test (dipstick) is required for women of childbearing potential.

^c Patients who complete surgery without complications will be randomized immediately after surgery.

^d Slit lamp examination of anterior chamber: cells score and aqueous flare (Tyndall effect) score; assessment of conjunctival hyperemia.

^e Global evaluation on a 4-point scale. Burning, stinging, blurred vision on a 4-point scale.

^f Second period of treatment will start after drug dispensation at Day 8

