2.2 BACKGROUND

Cataract is an ocular condition that causes vision impairment due to changes in opacity of the ocular lens. Cataract is an age-related condition, but smoking, ocular trauma, exposure to ultraviolet light, diabetes and drug-induced metabolic changes in the lens are risk factors for lens opacification causing cataract.¹

The only cure for cataract is a surgical procedure: the opaque lens is removed and replaced with an artificial intraocular lens.^{2, 3} Nowadays, the surgical procedure of choice is phacoemulsification with intraocular lens implantation.⁴ The technique, initially developed in 1967, is based on high-energy ultrasound to emulsify the cataractous lens nucleus, with the fragments being subsequently aspirated with an ultrasound probe. The corneal incision required for this technique is much

smaller (3 mm or less) than the limbal incision (usually an 11-mm incision between cornea and sclera) used in the past to remove the entire lens.²

As the surgical procedure has become less invasive, patients usually no longer require in-patient hospital care after surgery, with recovery usually uneventful and pain-free. Cataract surgery may however cause corneal trauma, ocular inflammation and ocular dryness, which can result in ocular irritation during the recovery period.⁵⁻⁷ These conditions may cause different types of ocular discomfort such as pain, burning, stinging, foreign body sensation, itchiness and glare in the operated eye. The incidence of ocular irritation symptoms experienced during the first postoperative hours may be as high as 98%.⁸

Conjunctival hyperemia, anterior chamber cells and flare, and cystoid macular edema are some possible signs of inflammation after cataract surgery.⁹ The severity of the inflammation varies from patient to patient. In many cases, inflammation is self-limiting, but drug therapy is used to shorten resolution time and alleviate ocular discomfort.¹⁰

Steroidal agents and non-steroidal anti-inflammatory drugs (NSAIDs) are used to prevent and treat postoperative inflammation occurring after surgery. Corticosteroids inhibit the lipoxygenase pathway leading to the leukotriene production and thus reduce tissue swelling and prevent edema.^{9,11} They have been used for decades to prevent ocular inflammation and many ophthalmic surgeons prefer a 1 to 6-week period of topical corticosteroids after cataract surgery.

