8 STUDY ASSESSMENTS AND PROCEDURES

8.1 SCHEDULE OF ASSESSMENTS

The following visits will be performed as listed in the SoA. Additional visits will be made available to patients in case of need.

Visit 1: Screening (to be performed not more than 28 days prior to surgery)

Upon signing the informed consent form each patient is uniquely identified by a patient ID number which is composed of the site number and a sequential number assigned automatically by the eCRF. Once assigned to a patient, the patient ID number will not be reused.

At screening, after obtaining signed written informed consent, inclusion/exclusion criteria will be checked and the following assessments will be performed/data collected:

- Demographics
- Medical history
- Use of concomitant medications

- Slit lamp examination
- Intraocular pressure
- Visual acuity
- Adverse events

Visit 2 - Day of surgery

Prior to surgery, inclusion/exclusion criteria will be rechecked, and the following assessments will be performed/data collected:

- Use of concomitant medications, including prophylactic pre-operative medications to be stopped before surgery
- Adverse events occurred after previous visit.

Women of childbearing potential will be required to undergo a urine pregnancy test (dipstick).

Patients who completed surgery without complications will be randomized to one of the two treatment arms and will be provided with study drug needed until visit at day 8 (first period of treatment) and a diary on which to record times of instillations.

Visit 3 - Visit on day 4 after 3 full days of treatment

On Day 4, patients should return their diaries to evaluate compliance. The following assessments will be performed/data collected on Day 4:

- Concomitant medications
- Slit lamp examination
- Evaluation of any ocular infections
- Total Ocular Symptom Score (TOSS)
- Ocular pain/discomfort
- Use of rescue therapy
- Intraocular pressure
- Local tolerability (global evaluation/burning, stinging, blurred vision)
- Adverse events occurred after previous visit

Visit 4 - Visit on day 8 after 7 full days of treatment

On Day 8, patients should return unused medication and completed diary to evaluate compliance and will receive a new supply of medication needed until end of study and a new diary. The second period of treatment will start after the new supply.

The following assessments will be performed/data collected on Day 8:

• Concomitant medications

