Sponsor: NTC S.r.l. Amended Protocol No.: LEVODESA_04-2017

- Slit lamp examination
- Evaluation of any ocular infections
- TOSS
- Ocular pain/discomfort
- Use of rescue therapy
- Intraocular pressure
- Local tolerability (global evaluation/burning, stinging, blurred vision)
- Adverse events occurred after previous visit

Visit 5 - Visit on day 15 after 14 full days of treatment (end of study)

On Day 15, patients should return unused medication and completed diary to evaluate compliance. The following assessments will be performed/data collected on Day 15:

- Concomitant medications
- Slit lamp examination
- Evaluation of any ocular infections
- TOSS
- Ocular pain/discomfort
- Use of rescue therapy
- Intraocular pressure
- Visual acuity
- Local tolerability (global evaluation/burning, stinging, blurred vision)
- Adverse events occurred after previous visit

END OF STUDY

After the end of study visit performed at day 15, patients will be managed according to standard routine practice applied by each center.

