8.3 SAFETY, TOLLERABILITY AND OTHER ASSESSMENTS

Safety will be monitored by evaluating all adverse events, especially increases in intraocular pressure (IOP) (measured at each visit following surgery) and drop in visual acuity assessed as per local clinical practice (measured on Day 15).

Local tolerability will be evaluated at all visits following surgery as follows:

- Global evaluation on a 4-point scale: 0 = no intolerability, 1 = mild intolerability, 2 = moderate intolerability, 3 = maximum intolerability.
- Burning, stinging, blurred vision on a 4-point scale: 0 = none, 1 = mild, 2 = moderate, 3 = severe.

Compliance will be evaluated on Day 4, Day 8 and Day 15 by means of a patient diary in which the instillations are to be recorded.

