9.4.4 SAFETY ANALYSES

Adverse Events

All safety analyses will be performed on the Safety set. No missing data handling approach will be applied.

The incidence of Adverse Events (AEs) and Serious Adverse Events (SAEs) recorded throughout the study will be presented overall and by treatment group. According to the onset date of the event, AEs will be defined as follows:

- Treatment-emergent AE: event with an onset date after treatment initiation
- Non-treatment-emergent AE: event with an onset date between informed consent and treatment initiation

Non-treatment-emergent AEs will be listed only.

Treatment-emergent AEs will be summarized by MedDRA dictionary system organ class and preferred term. A summary of treatment-emergent AEs by system organ class, preferred term and

severity will be also provided. All related treatment-emergent AEs, treatment-emergent SAEs, treatment-emergent AEs with an outcome of death, treatment-emergent AEs leading to treatment discontinuation will be summarized by MedDRA dictionary system organ class and preferred term and will also be listed.

All deaths will be listed together with all their details.

Intraocular pressure

The number of patients with a significant increase (> 6 mmHg) in intraocular pressure will be recorded and summarized descriptively. The comparison between test treatment and standard treatment in the incidence of significant increase of IOP will be made by means of 95% CI of the difference between treatments.

Visual acuity

The number of patients with a decrease in visual acuity measured as per local clinical practice will be recorded and summarized descriptively. The comparison between test treatment and standard treatment in the drop of visual acuity will be made by means of 95% CI of the difference between treatments.

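### Visual-acuity safety analysis: decrease can only be judged against a reading taken before the cataract was removed; a supportive Day 15 comparison adjusted for screening acuity would be more sensitive to broad or moderate losses

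*Combined protocol and SAP*

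**What the plan says.** Visual acuity is a named safety endpoint (Section 3). Section 9.4.4 plans two things for it. First, a count: "The number of patients with a decrease in visual acuity measured as per local clinical practice will be recorded and summarized descriptively". Second, a between-arm comparison: "The comparison between test treatment and standard treatment in the drop of visual acuity will be made by means of 95% CI". It states no reference visit, minimum change, eye or common scale. The neighboring IOP analysis does carry a cut-off: "The number of patients with a significant increase (> 6 mmHg) in intraocular pressure will be recorded and summarized descriptively".

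The schedule (Sections 1.3 and 8.1) has two acuity readings. One is at "Visit 1: Screening (to be performed not more than 28 days prior to surgery"), when surgery has not yet been performed. The other is at "Visit 5 - Visit on day 15 after 14 full days of treatment (end of study"). Section 8.3 agrees, referring to a "drop in visual acuity assessed as per local clinical practice (measured on Day 15"). Between the two readings, as Section 2.2 puts it, "the opaque lens is removed and replaced with an artificial intraocular lens".

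**The concern.** The only scheduled reading before Day 15 was taken through a cataract, so it is the only available reference for a decrease. Surgery is expected to improve acuity. A loss after surgery becomes visible in the count only when it exceeds that gain; smaller losses are hidden in eyes that still see better than at screening. A confidence interval close to zero could then look reassuring even though the arms differ in Day 15 acuity. Section 8.3 singles out acuity drop within safety monitoring, so the analysis should be able to show one.

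**Working it through.** **Inputs.** From the documents: two acuity readings (Sections 1.3, 8.1, 8.3), 400 patients per arm and about 10% dropout (Section 9.2), hence 400 × 0.9 = 360. The documents give no acuity distribution and no figure for this analysis that could be reproduced. Everything else is assumed, in logMAR (higher is worse):

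- screening mean 0.3 / 0.4 / 0.5 with SD 0.20 / 0.25 / 0.30, paired with Day 15 mean 0.08 / 0.09 / 0.10
- Day 15 SD 0.15 or 0.25; correlation r of 0.3 or 0.5; n of 360 or 400 per arm

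This makes 3 × 2 × 2 × 2 = 24 paired cases. A wider set crosses three screening means, three screening SDs and Day 15 means of 0.08 and 0.10 with the same r, SD and n, giving 144 cases.

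**Mechanism.** If surgery gains G and the eye then loses L, the net change is G − L. The eye is counted only if L > G. This needs no assumed figure.

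**Formulas.** With sb and sd the screening and Day 15 SDs:

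- SDchange = √(sb² + sd² − 2·r·sb·sd)
- P(counted) = 1 − Φ((t − (Day 15 mean + loss − screening mean)) / SDchange), where t is the minimum change (0 if any decrease counts)
- count: unpooled two-proportion z, two-sided 5%
- unadjusted mean change: SE = SDchange·√(2/n)
- adjusted Day 15: SE = sd·√(1 − r²)·√(2/n)
- if only a fraction f of test-arm eyes loses h, f(1 − f)h² is added to that arm's variance in the two mean comparisons

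**One case in full** (screening 0.4, SD 0.25; Day 15 0.09, SD 0.15; r 0.3; n 360; all test-arm eyes lose 0.05).

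- SDchange = √(0.0625 + 0.0225 − 0.0225) = 0.25.
- Count: control 1 − Φ(0.31/0.25) = 10.7%; test 1 − Φ(0.26/0.25) = 14.9%. The difference is 0.0417 and its SE 0.0249, so the CI excludes zero 39% of the time.
- Mean change: SE 0.25 × √(2/360) = 0.0186; 0.05/0.0186 = 2.68, giving 77%.
- Adjusted: residual SD 0.15 × √0.91 = 0.143; SE 0.0107; 0.05/0.0107 = 4.69, giving over 99%.

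**Share of affected eyes that are counted** (loss 0.2, Day 15 SD 0.15, r 0.3, three scenarios): 25-46% if any decrease counts, 15-29% with a 0.1 minimum, 9-15% with a 0.2 minimum.

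**Chance that the 95% CI excludes zero, 24 paired cases, any decrease counted:**

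| True harm in test arm | Count | Adjusted Day 15 |
|---|---|---|
| All eyes lose 0.05 | 25-71% | 80% to over 99% |
| All eyes lose 0.02 | 8-16% | 20-59% |
| 10% lose 0.3 | 19-63% | 37-83% |

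Unadjusted mean change detects the 0.05 shift 53-98% of the time. In these three settings the count never leads, in the paired or the crossed set, with a minimum change of 0, 0.1 or 0.2.

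**Rare, large losses: cases in which the count leads the adjusted comparison, by minimum change 0 / 0.1 / 0.2:**

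| True harm | Of 24 paired | Of 144 crossed |
|---|---|---|
| 5% lose 0.5 | 0 / 8 / 12 | 26 / 50 / 68 |
| 3% lose 0.8 | 0 / 4 / 22 | 20 / 56 / 100 |

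**The case against.** **The comparison sentence is ambiguous.** For IOP, Section 9.4.4 compares incidence; for acuity it compares the drop. That can mean the size of the change, in which case a between-arm estimate is already planned and, under randomization, it targets the same effect as a Day 15 comparison. This stands, and it narrows the gap. It does not close it: 53-98% against 80% to over 99% for the 0.05 shift.

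**Safeguards exist.** Deterioration or a new clinically relevant finding is recorded as an AE (Sections 7.1, 8.4.4), AEs are tabulated by arm, and listings are planned. A reader might infer that acuity loss would go unrecorded; the documents do not support that. But the AE route takes the condition at screening as baseline and depends on clinical notice. Neither it nor the general summaries in Section 9.4.1 specify a between-arm estimate of Day 15 acuity.

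**The largest advantage is for the smallest harm.** A 0.05 logMAR shift is a factor of 10^0.05 = 1.12, and nothing in the documents suggests that such a shift will occur; both arms contain dexamethasone 1 mg/ml. This is fair. The advantage for 10% losing 0.2 also depends on inputs: 10-31% against 20-54% with the paired inputs, but 15-45% against 19-42% (no clear winner) if mean gain is set at 0.2-0.4, n at 400 per arm, and change SD and residual SD are each varied over 0.15-0.25 independently.

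**The missing eye is minor.** Exclusion criterion 8 is an eligibility check on the contralateral eye; no Day 15 contralateral reading is specified and bilateral surgery is excluded.

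**Not everything was tested.** Adjustment for about 80 centers (800/80 = 10 patients each) was not examined. The SD 0.25 cases add noise only to the Day 15 reading, although both visits use local practice.

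**Conclusion.** The point holds as a loss of sensitivity. The screening reference follows from the schedule, and the shrinkage of the count toward zero follows from the mechanism; its size rests wholly on assumed acuity figures. On either reading of the comparison sentence, adjustment for screening acuity gives better sensitivity to broad losses and, over most of the assumed range, to moderate ones.

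Three stronger inferences are not supported. The count is not biased toward an arm, because randomization gives both arms the same expected surgical gain. The non-inferiority conclusion is not affected, because no decision rule uses acuity. The adjusted comparison should not replace the count, which is often as good or better for rare, large losses, mainly when a minimum change is set. Nor does the point bear on endophthalmitis, which has its own endpoint: at the 0.03-0.3% in Section 2.2, 400 × 0.0003 = 0.12 to 400 × 0.003 = 1.2 cases per arm are expected, too few for either acuity analysis to detect a difference.

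This is a cheap improvement to a safety summary, not a flaw in the trial's main inference.

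**What to change.** In Section 9.4.4 (Visual acuity), or in the SAP before database lock:

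1. Keep the count and its 95% CI.
2. Add a supportive between-arm comparison of Day 15 study-eye acuity, converted to logMAR where the recorded data allow, adjusted for screening acuity and country (or center as a random effect), with a 95% CI.
3. Report, by arm, how many readings could not be converted.
4. As clarification only, state the eye, the reference visit, whether the drop means the count or the size of the change, and any minimum change. A minimum directs the count toward rare, large losses and lowers its capture of moderate ones (for a 0.2 loss, from 25-46% to 9-15% with a 0.2 minimum).

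Cost: SAP wording, one standard model and a conversion table; no new visits. Criterion 8 already equates 20/80 with decimal 0.25, which is −log10(0.25) = 0.60 logMAR. The downside is conversion noise from local-practice measurement at both visits. The documents do not say whether chart type and correction status are recorded; if they are not, two eCRF fields would be needed, or some readings will stay unconverted.

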9.4.5 TOLERABILITY ANALYSES

Local tolerability will be analyzed descriptively. Two-sided 95% CI will also be provided.

9.4.6 ANALYSIS OF COMPLIANCE

For each treatment, compliance will be evaluated through an evaluation of the number of instillations recorded in the patient diary.

9.4.7 BASELINE DESCRIPTIVE STATISTICS

Medical history and demographic features will be summarized descriptively. No statistical test will be performed for between-group differences in demographic and baseline features.

9.4.8 PLANNED INTERIM ANALYSES

No interim analysis is planned.

9.4.9 SUB-GROUP ANALYSES

No sub-group analyses are planned.

9.4.10 TABULATION OF INDIVIDUAL PARTICIPANT DATA

Patient listings will be provided.

9.4.11 EXPLORATORY ANALYSES

No exploratory analyses are planned.

10 SUPPORTING DOCUMENTATION AND OPERATIONAL CONSIDERATIONS

10.1 REGULATORY, ETHICAL, AND STUDY OVERSIGHT CONSIDERATIONS

10.1.1 INFORMED CONSENT PROCESS

10.1.1.1 CONSENT AND OTHER INFORMATIONAL DOCUMENTS PROVIDED TO PARTICIPANTS

Consent forms describing in detail the study intervention, study procedures, and risks are given to the participant and written documentation of informed consent is required prior to starting intervention/administering study intervention.

10.1.2 CONSENT PROCEDURES AND DOCUMENTATION

Informed consent is a process that is initiated prior to the individual's agreeing to participate in the study and continues throughout the individual's study participation. Consent forms will be approved by the IRB/IEC and the participant will be asked to read and review the document. The investigator will explain the research study to the participant and answer any questions that may arise. A verbal explanation will be provided in terms suited to the participant's comprehension of the purposes, procedures, and potential risks of the study and of their rights as research participants. Participants will have the opportunity to carefully review the written consent form and ask questions prior to signing. The participants should have the opportunity to discuss the study with their family or surrogates or think about it prior to agreeing to participate. The participant will sign the informed consent document prior to any procedures being done specifically for the study. Participants must be informed that participation is voluntary and that they may withdraw from the study at any time, without prejudice. A copy of the informed consent document will be given to the participants for their records. The informed consent process will be conducted and documented in the source document (including the date), and the form signed, before the participant undergoes any study-specific procedures. The rights and welfare of the participants will be protected by emphasizing to them that the quality of their medical care will not be adversely affected if they decline to participate in this study.

10.1.3 STUDY DISCONTINUATION AND CLOSURE

This study may be temporarily suspended or prematurely terminated if there is sufficient reasonable cause. Written notification, documenting the reason for study suspension or termination, will be provided by the suspending or terminating party to study participants, investigator, Sponsor and regulatory authorities. If the study is prematurely terminated or suspended, the Principal Investigator will promptly inform study participants, the IRB/IEC, Regulatory Authorities and Sponsor, and will provide the reason(s) for the termination or suspension. Study participants will be contacted, as applicable, and be informed of changes to study visit schedule.

Circumstances that may warrant termination or suspension include, but are not limited to

- Determination of unexpected, significant, or unacceptable risk to participants
- Insufficient compliance to protocol requirements
- Data that are not sufficiently complete and/or evaluable
- Determination of futility

The study may resume once concerns about safety, protocol compliance, and data quality are addressed, and satisfy the Sponsor, IEC and regulatory authorities.

10.1.4 CONFIDENTIALITY AND PRIVACY

Participant confidentiality and privacy is strictly held in trust by the participating investigators, their staff, and the Sponsor and their interventions. This confidentiality is extended to cover testing of biological samples (urine for pregnancy test) in addition to the clinical information relating to participants. Therefore, the study protocol, documentation, data, and all other information generated will be held in strict confidence. No information concerning the study or the data will be released to any unauthorized third party without prior written approval of the Sponsor.

All research activities will be conducted in as private a setting as possible.

The study monitor, other authorized representatives of the Sponsor, representatives of the IRB/IEC and regulatory agencies may inspect all documents and records required to be maintained by the investigator, including but not limited to, medical records (office, clinic, or hospital) and pharmacy records for the participants in this study. The clinical study site will permit access to such records.

The study participant's contact information will be securely stored at each clinical site for internal use during the study. At the end of the study, all records will continue to be kept in a secure location for as long a period as dictated by the reviewing IRB/IEC, Institutional policies, or Sponsor requirements.

Study participant research data, which is for purposes of statistical analysis and scientific reporting, will be transmitted to and stored at the Contract Research Organization (CRO) (OPIS s.r.l.) working on behalf of the Sponsor. This will not include the participant's contact or identifying information. Rather, individual participants and their research data will be identified by a unique study identification number. Only the study center will be able to link the study ID number to the

patient's identity. The study data entry and study management systems used by clinical sites and by OPIS research staff will be secured and password protected.

